#### 5. SAMPLE SIZE CONSIDERATIONS

Sample size calculations were produced using the proc power function in SAS Version 9.4. These were conducted to achieve 80% power to detect a difference in the active arm versus the control group at the 5% level of significance. Based on a mean of 99mg/L in the control group and a common standard deviation of 62mg/L derived from the literature [2, 3], a total sample size of 90 participants would provide sufficient power to detect a greater than a 40% relative difference for CRP in the dornase alfa group compared to the control group. Given the reported average values in severe and non-severe participants and on clinical observations from COVID-19 patients, this difference would be achievable and clinically relevant.

This study will use existing data collected at UCLH from participants admitted with COVID-19 as a comparator group. Participants in the database will be selected to act as controls as follows:

- Apply the inclusion and exclusion criteria of the COVASE study where the appropriate data are available
- Additional selection to identify closest matches

This will give the correct ratio of active versus comparator (ratio of 1:2). To achieve the required power, this would result in 30 participants in the active treatment group and at least 60 in the control. An additional 10 participants will be recruited as a control for the exploratory objectives

#### **Exploristics Limited**

Identifier: EXP20012 Clinical Study Identifier: 132333

and to compare the characteristics of enrolled participants with the historical controls. This gives a total of 40 participants enrolled in the study and 60 historical controls.

Participants who drop out of the study will be replaced so the sample size relates to the number of evaluable participants required.

A re-estimation of the sample size will be carried following an interim analysis when 12 randomised participants have completed Day7 follow up. This sample size calculation will be carried out using a promising zones approach [1] (see Section 12 for details).

### 6. ANALYSIS POPULATIONS

The primary analysis will be conducted using the primary analysis population and is based on the ITT principle. Details on subjects enrolled but not included in the analysis populations will be presented as part of the CONSORT diagram.

# 6.1 Primary analysis population (Intention to treat)

The primary analysis population will be all evaluable patients randomised to BAC + dornase alfa or BAC only who have at least one post-baseline CRP measurement, as well as matched historical comparators.

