8.8 Discontinuation/withdrawal of participants

In consenting to participate in the trial, participants are consenting to trial treatment, assessments, follow-up and data collection.

Discontinuation of trial treatment for clinical reasons

A participant may be withdrawn from trial treatment whenever continued participation is no longer in the participant's best interests, but the reasons for doing so must be recorded. Reasons for discontinuing treatment may include:

- Alternative clinical diagnosis emerges (no longer considered to have primary COVID-19 lung disease).
- Disease progression whilst on therapy.
- Unacceptable toxicity.
- Intercurrent illness which prevents further treatment.
- Patients withdrawing consent to further trial treatment.
- Any alterations in the participant's condition which justifies the discontinuation of treatment in the Cl's or designee's opinion.
- Persistent non-compliance to protocol requirements.
- Participant is put on end of life pathway and dies prior to dosing.

The decision to withdraw a participant from treatment must be recorded in the CRF and medical notes, and the sponsor when required should be notified in writing.

Participant withdrawal from trial treatment or follow-up

If a participant expresses their wish to withdraw from trial treatment or follow-up, sites should explain the importance of remaining on trial follow-up and seek permission to allow use of routine follow-up data to be used for trial purposes. The importance of safety follow-up should be emphasised to the participant in the Participant Information Sheet.

The decision of the participant to withdraw from treatment or follow-up must be recorded in the CRF and medical notes.

The participant may withhold their reason for withdrawal however, if the participant gives a reason for their withdrawal, this should be recorded.

Withdrawal of consent to data collection

If a participant explicitly states that they do not wish to contribute further data to the trial their decision will be respected and recorded in the CRF and medical notes.

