#### 2.2.2 Secondary Endpoints

Secondary endpoints include, but are not limited to:

- Levels of acute phase reactant CRP over 35 days follow-up
- Length of hospitalisation from baseline (days)
- Survival at Day35, mortality data collected from EPIC database for both HCs and randomised individuals
- White blood cell count over 7 days follow-up
- Neutrophil count over 7 days follow-up
- Lymphocyte count over 7 days follow-up
- Monocyte count over 7 days follow-up
- Eosinophil count over 7 days follow-up
- Basophil count over 7 days follow-up
- Procalcitonin over 7 days follow-up
- D-dimer count over 7 days follow-up
- Blood pressure over 7 days follow-up
- Pulse rate over 7 days follow-up
- Temperature over 7 days follow-up
- Respiratory rate over 7 days follow-up
- Time on Oxygen over 7 days follow-up
- Time on Oxygen over 35 days follow-up
- Proportion of individuals with Pneumonia over 7 days follow-up
- Ordinal score (WHO scoring tool) over 7 days follow-up (including randomized individuals only)
- Proportion of individuals on Mechanical Ventilation (MV) over 7 days follow-up
- Time on MV over 7 days follow-up
- Length of ICU stay (hours) over 7 days follow-up
- Proportion of individuals with Pneumonia over 35 days follow-up
- Proportion of individuals on Mechanical Ventilation (MV) over 35 days follow-up
- Time on MV over 35 days follow-up
- Length of ICU stay (hours) over 35 days follow-up

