#### **11.1 Primary endpoint analysis**

#### **Exploristics Limited**

### Identifier: EXP20012 Clinical Study Identifier: 132333

The primary endpoint will be compared between groups using a repeated measures mixed model, adjusted for age, gender, BMI, baseline CRP value (defined as the last CRP measurement prior to randomisation, or the first CRP following Dexamethasone for HCs), time from baseline, and whether they have a key comorbidity, defined as one or more of hypertension, diabetes or cardiovascular disease. An interaction between treatment and time from baseline will also be included in the model. CRP measurements more than 7 days after randomisation (or date of first CRP measurement following Dexamethasone initiation for HCs) will be removed from the analysis, so the comparison is over 7 days.

Due to the treatment by time interaction effect being included in the model, examining the treatment effect alone would be an inappropriate comparison, therefore the least squares means and 95% confidence intervals at the mean follow-up time will be compared between arms, which will take into account both the treatment effect and the treatment by time interaction. These means will be presented on the real scale, e.g. taking the antilog of the least squares mean if the dependent variable has been log-transformed. The difference between the least squares means (on the scale the model was fitted) and the standard error of the difference will be used to generate a treatment z-score, which will be compared against the normal distribution with mean 0 and variance 1, to obtain the two-sided p-value.

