For the following secondary endpoints, a survival analysis will be conducted. The number of events by arm will be compared. The time to event data will be censored at 28 days post last dose (Day35) for the randomised participants and at 35 days after baseline, or the date of the last electronic record, whichever is earlier, for the historical control group. If median time-to-event times exist, the Kaplan-Meier method will be used to estimate the median time-to-event times and the associated 95% confidence intervals. The survival model will include treatment as a stratification variable and significance assessed using a log-rank test. A Cox proportional hazards model will be used to generate a hazard ratio and associated confidence intervals, adjusting for age, baseline CRP value (defined as the last CRP measurement prior to randomisation, or the first CRP following Dexamethasone for HCs) and treatment as a main effect. For the time to discharge from hospital analysis, data will be censored if the participant dies prior to discharge at the date of death.

- Survival at Day35
- Time to discharge from hospital from baseline (days) to Day 35

For the following secondary endpoint, a logistic regression model will be fitted, with age, gender, BMI baseline CRP value (defined as the last CRP measurement prior to randomisation, or the first CRP

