## **Exploristics Limited**

Identifier: EXP20012

Clinical Study Identifier: 132333

The secondary outcome analysis will use the primary analysis population.

Note: if models fail to converge or have evidence of over-fitting, covariates will be removed from the models in the following order: serious condition, Sex, Age, BMI, baseline value of measurement.

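### The SAP's intention-to-treat population drops randomised patients without a post-baseline CRP, but not historical controls, and is then used for survival, ventilation and ICU endpoints that need no CRP

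*SAP*

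**What the plan says.** SAP section 6 states: "The primary analysis will be conducted using the primary analysis population and is based on the ITT principle". SAP 6.1, whose heading carries the intention-to-treat label, then limits the randomised patients to evaluable ones "who have at least one post-baseline CRP measurement, as well as matched historical comparators". The controls are added after the condition, which as worded does not reach them. Protocol 11.3.1 has no CRP condition in its primary population; the SAP introduced it.

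At the end of SAP 11.2: "The secondary outcome analysis will use the primary analysis population". The endpoints listed there include Day 35 survival, time to discharge, mechanical ventilation, pneumonia, ICU stay, time on oxygen and length of hospitalisation.

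SAP 2.2.2 defines the survival endpoint as "Survival at Day35, mortality data collected from EPIC database for both HCs and randomised individuals". For the controls, SAP 11.2 censors survival "at 35 days after baseline, or the date of the last electronic record, whichever is earlier, for the historical control group", so their clock runs from baseline. Baseline CRP is "defined as the last CRP measurement prior to randomisation, or the first CRP following Dexamethasone for HCs" (SAP 11.1).

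Among the reasons for stopping treatment, Protocol 8.8 lists: "Participant is put on end of life pathway and dies prior to dosing".

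**The concern.** None of the clinical endpoints needs a later CRP. Using the CRP-restricted population for them means that a randomised patient enters the survival analysis only by living, and staying under observation, until a blood test after baseline. A historical control enters at baseline. Early deaths are thus removed from the dornase alfa arm and kept in most of the comparator group, which is a form of immortal time.

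The removed outcomes would mostly be known, since mortality comes from EPIC for both sources. The same holds for a patient who withdraws from treatment or follow-up before a further CRP but does not refuse use of their data. The resulting hazard ratio would be reported from a population labelled intention to treat.

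**Working it through.** **The plan's own figure.** The SAP's total of 90 reproduces. With a two-sided t-test at 5%, a difference of 0.40 × 99 = 39.6 mg/L, SD 62 and 30:60 patients, the noncentrality is 39.6 / (62 × √(1/30 + 1/60)) = 2.86 and power is 80.65%. At 29:58 power is 79.3%, so 90 is the smallest 1:2 total reaching 80%. This confirms how the inputs were read; it does not bear on who is analysed.

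**Who is in the survival analysis, as the SAP is worded**
- Randomised patient, dies before any post-baseline CRP: out (SAP 6.1 with 11.2), in either randomised arm.
- Historical control, dies equally soon after baseline: in. No condition is written for controls. Deaths before the first CRP after dexamethasone do not count, just as deaths before randomisation do not.
- Matching: the propensity model in SAP 11 uses everyone randomised to dornase alfa and takes two controls for each. Nothing says that those controls leave when their matched patient is excluded.

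**How wide the window is.** CRP is due on Day 1, 3, 5 and 7 (Protocol 5.1 and 8.4.1). Whether the Day 1 draw is post-baseline depends on whether it follows randomisation. The exposed period is therefore roughly the first one to three days.

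**Size for deaths.** Inputs: true Day 35 mortality *p*, equal in all groups, 4 to 15% (Protocol section 3, for confirmed COVID-19 pneumonia); *f*, the share of deaths before the first post-baseline CRP, **assumed** 10, 20 or 33%.

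- Apparent mortality in a randomised arm: *p*(1 − *f*) / (1 − *pf*).
- Its odds are *p*(1 − *f*) / (1 − *p*), so the spurious odds ratio against historical controls is 1 − *f*, whatever *p* is.
- Expected exclusions among 40 randomised: 40 × *p* × *f*.

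| *f* | Apparent mortality if *p* = 15% | OR v 60 historical controls | OR v all 70 comparators | Expected exclusions of 40, *p* = 4% to 15% |
|---|---|---|---|---|
| 10% | 13.7% | 0.90 | 0.91 | 0.16 to 0.60 |
| 20% | 12.4% | 0.80 | 0.82 | 0.32 to 1.20 |
| 33% | 10.6% | 0.67 | 0.70 | 0.53 to 1.98 |

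The 70 comparators are 60 historical controls plus 10 randomised to best available care, whose early deaths are also removed; this is why the pooled odds ratios lie slightly closer to 1.

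**In whole patients.** Take 5/30 dornase alfa and 10/60 historical-control deaths, both 16.7%. Removing one early dornase alfa death gives 4/29 = 13.8% and an odds ratio of (4/25) / (10/50) = 0.80. Removing two gives 3/28 = 10.7% and (3/25) / (10/50) = 0.60.

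**The case against.** The strongest reply is that very few patients can be affected. Entry requires stable saturation of at least 94% on supplementary oxygen and excludes anyone needing ventilation at screening. CRP is also measured routinely, daily or on alternate days. Protocol 8.8 asks sites to seek permission to use routine data after withdrawal, so stopping treatment does not by itself remove CRP values. The patient in Protocol 8.8 who dies before dosing appears in a list of reasons for stopping treatment; the entry does not show that such a patient lacks a post-baseline CRP. All of this stands, and it limits the size.

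The SAP also has safeguards. Deaths are compared in a safety population of all randomised patients (6.4, 11.4), exclusions appear in the CONSORT diagram (6), all available data enter the models (9.1), and secondary analyses are called descriptive (8.4). These do not repair the comparison. The safety population has no historical controls, a CONSORT diagram only discloses, and 9.1 does not override a population definition. SAP 11.2 still plans a log-rank test and a Cox hazard ratio.

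It is fair to add that SAP 6.1 is silent on controls; nothing states outright that those without a later CRP stay in. But if the condition was meant for them too, survival would still be conditioned on a later blood test.

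A reader might infer more than the documents support:
- *That early discharges are dropped, biasing time to discharge and length of stay.* Protocol 8.4.1 and Appendix 1 schedule a CRP before discharge, so a discharged patient should have one.
- *That the primary result is biased.* A patient without a post-baseline CRP has no outcome to contribute to the CRP model.
- *That a large distortion is likely.* For example, moving one of three deaths into the window turns 3/30 v 6/60 into 2/29 v 6/60, a risk ratio of 0.69. That assumes a third of deaths fall in one to three days, and the approximate 95% interval, 0.15 to 3.2, is far wider than the shift.

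**Conclusion.** The concern holds for the secondary clinical endpoints and should be fixed. As worded, the SAP removes known early outcomes of randomised patients while those of historical controls count from baseline, under an intention-to-treat label. For deaths the direction favours dornase alfa against the 60 historical controls. The condition is the same in both randomised arms, so no such asymmetry arises between them. No direction is claimed for ventilation or ICU stay.

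The expected number excluded is small, about 0.2 to 2 of 40. The spurious odds ratio of 0.90 to 0.67 rests on the assumed 10 to 33% share of early deaths, on equal true mortality, and on applying the protocol's general pneumonia mortality to this selected population. With so few deaths, a single exclusion moves the estimate visibly, though well within its sampling error.

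**What to change.** In SAP 6.1 and 11.2:
- Confine the post-baseline CRP condition to the CRP models.
- Analyse survival and the other non-laboratory clinical endpoints in all randomised patients by allocated arm, plus all matched historical controls, from baseline. Include patients never dosed or withdrawn from treatment, and leave out only data for which consent to use was withdrawn.
- Where a laboratory endpoint needs a post-baseline value, require it for that endpoint and apply the same condition to historical controls.

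The cost is SAP wording and one extra population flag; mortality from EPIC is already planned for both sources. The downside is that the number analysed will differ between the CRP and clinical tables, which a footnote can explain.

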### 6.2 Per protocol population

The per protocol (PP) population will be all evaluable patients randomised to BAC + dornase alfa or BAC only, as well as matched historical comparators, excluding important protocol violations. Important protocol violations will be defined as:

- Initiated dornase-alfa prior to Dexmathasone.
- Withdrew from the study prior to 7 days follow-up.
- Discontinued the study drug prior to discharge from hospital or 7 days follow-up.

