11.3.4 Sensitivity and other planned analyses

All primary and secondary analyses will be repeated using the primary analysis population and the per protocol population. The use of the per protocol population is only as a sensitivity analysis to understand the impact of non-compliance.

This study utilises a combination of enrolled and randomised participants, historical controls and banked biosamples. Descriptive statistics will be produced for key baseline variables for all data sources within the comparator population. These will be used to evaluate the comparability of the source data.

There are planned subgroup analyses that relate to secondary objectives. A comparison of the secondary endpoint, time on MV, between treatment groups will be conducted only in participants that received MV. Other subgroup analyses may be performed but these are considered to be exploratory.

Further exploratory analyses are planned for the exploratory endpoints in the study. These analyses will follow the same principles and considerations with regards to the application of statistical approaches for specific data types and data structures. The exploratory analyses will use the exploratory analysis population.

Full details of the planned statistical analysis will be presented in a separate Statistical Analysis Plan (SAP). This will be finalised prior to database lock. The results from all analyses will be presented in the form of tables, figures and listings.

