#### Figure 1: COVASE Trial Schematic

Participants will be screened, consented, enrolled and randomised up to 3 days after they are admitted to the hospital. They will be randomised in a 3:1 ratio to receive BAC + dornase alfa or BAC alone. A total of 40 participants will be enrolled (30 to receive BAC plus dornase alfa and 10 to receive BAC). On Day1 to Day7 of the trial, participants randomised to the active arm, will receive 2.5mg BID nebulised dornase alfa in addition to BAC. On Day1, Day3, Day5 and Day7, blood samples will be drawn in both trial arms in order to test pharmacodynamic endpoints (PD), biomarkers and clin labs. Clinical assessments will be undertaken daily (as per UCLH clinical guidelines). Participants will be followed until discharge or death or a maximum of 28 days follow-up.

A sample size re-estimation is planned when 12 randomised participants have completed Day7 of follow-up. This analysis will ensure that the assumptions made in the sample size calculation remain valid. However, if the variability is higher than expected then up to an additional 10 participants will be enrolled and treated with dornase alfa (up to 48 participants in total).

CRP has been chosen as the Primary Endpoint because it is a clinically important marker of inflammation and is used to make clinical treatment decisions. In addition, it is induced by the overexuberant inflammation mediated by the NETs and inflammatory histones. CRP is a prognostic marker and correlates with clinical symptoms, inflammation and response to therapy.

Based on clinical judgement, it may be decided to keep some participants on treatment for up to 14 days. In particular, if participants have significant benefits from therapy, but show relapses of the COVID-19 inflammatory state (rising CRP and increasing oxygen requirements in the absence of bacterial infection), on completing 7 days of treatment, then the medical team have the choice of

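### The per-protocol exclusions in SAP 6.2 fall almost only on dornase alfa patients and take in stops for deterioration, so that sensitivity analysis is expected, though not certain, to favour dornase alfa

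*SAP*

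**What the plan says.** SAP 6.2 builds the per-protocol set from the evaluable randomised patients and the matched historical controls, then removes three kinds of violation:

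- an early stop of treatment: "Discontinued the study drug prior to discharge from hospital or 7 days follow-up"
- the order of the two drugs, where dornase alfa was started before dexamethasone
- loss from the trial itself: "Withdrew from the study prior to 7 days follow-up"

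The reason for stopping or withdrawing plays no part in the rule.

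Protocol 8.8 gives reasons for which trial treatment may be stopped. They include "Disease progression whilst on therapy", "Unacceptable toxicity" and intercurrent illness. Persistent non-compliance is a separate entry in the same list.

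Protocol 11.3.4 gives the set its role: "All primary and secondary analyses will be repeated using the primary analysis population and the per protocol population". It limits the purpose: "The use of the per protocol population is only as a sensitivity analysis to understand the impact of non-compliance".

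SAP section 3 links the primary endpoint to clinical course: "CRP is a prognostic marker and correlates with clinical symptoms, inflammation and response to therapy".

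The primary analysis itself follows the ITT principle (SAP section 6).

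**The concern.** A per-protocol analysis is a useful check only if the patients it drops are not selected by outcome in one group alone. Here a dornase alfa patient who gets worse and stops treatment is removed. On a literal reading, so is one who dies on treatment before Day 7. A control who gets worse over the same days has no study drug to stop and stays in. Since CRP tracks clinical course, the patients removed are likely to be those with high CRP.

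The result could then look better for dornase alfa without any drug effect. Readers would be inclined to take it as confirming the primary analysis. This matters more than usual because the trial is open-label and most comparators are historical.

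**Working it through.** **1. The plan's own figure.** Inputs from SAP section 5: control mean 99 mg/L, SD 62 mg/L, 40% relative difference, 80% power, 5% level, 1:2 allocation. The two-sided test is from SAP 11.1.

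- Difference = 0.40 × 99 = 39.6 mg/L, or 39.6/62 = 0.639 SD.
- Noncentrality at 30:60 = 0.639 × √(30 × 60/90) = 2.86, giving t-test power of 80.7%. At 29:58 it is 79.3%.

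The stated total of 90 is reproduced. The documents give no figure for per-protocol exclusions.

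**2. Who can be excluded.** Planned numbers are from SAP section 12.

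| Criterion | Dornase alfa (30) | Randomised BAC (10) | Historical controls (60) |
|---|---|---|---|
| Dornase alfa before dexamethasone | yes | no | no |
| Study withdrawal before 7 days | yes | yes | no |
| Study drug stopped early | yes | no | no |

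None of the criteria can reach 60 of the 70 comparators (86%).

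**3. Illustrative size.** Assume no drug effect and the same disease course in all groups. Let k of 30 dornase alfa patients stop, with mean CRP e SD above the other 30 − k. Both k and e are assumptions.

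- Fall in the active mean after removal = (k/30) × e × 62 mg/L.
- With n = 30 − k, noncentrality = (k/30) × e × √(70n/(n + 70)).
- Two-sided rejection = Φ(noncentrality − 1.96) + Φ(−noncentrality − 1.96).

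Example with k = 5, e = 1: fall = (5/30) × 62 = 10.3 mg/L; noncentrality = 0.1667 × √(70 × 25/95) = 0.1667 × 4.292 = 0.715; rejection = 0.107 + 0.004 = 11.0%.

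| k | e (SD) | Fall (mg/L) | Share of 39.6 mg/L | Rejection at 5% |
|---|---|---|---|---|
| 3 | 0.5 | 3.1 | 8% | 5.6% |
| 5 | 0.5 | 5.2 | 13% | 6.5% |
| 8 | 0.5 | 8.3 | 21% | 8.5% |
| 3 | 1 | 6.2 | 16% | 7.3% |
| 5 | 1 | 10.3 | 26% | 11.0% |
| 8 | 1 | 16.5 | 42% | 19.4% |

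With only 1 or 2 stopping at 1 SD, rejection is 5.3% or 6.0%.

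**4. Check by simulation.** This used 20,000 trials per scenario, 30 against 70, an unadjusted t-test and no drug effect. With 10% stopping at 1 SD, significant results favouring dornase alfa occur 6.0% of the time; with 20% stopping, 12.2%. The nominal rate in that direction is 2.5%, and the ITT comparison stays at about that level.

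**5. A force in the other direction.** Patients who started dornase alfa before dexamethasone may show a dexamethasone-related fall in CRP after baseline. Removing them would count against dornase alfa. If they were 10% of the arm with CRP 0.5 SD lower, the offset would be 0.10 × 0.5 × 62 = 3.1 mg/L, which cancels the smallest row of the table.

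**6. Replacement.** Protocol 8.9 lets a withdrawn participant be replaced in the same arm. If 30 remain after replacement, k/30 becomes k/(30 + k) and n becomes 30. At 1 SD the rejection rates become about 7%, 10% and 16%.

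**The case against.** The per-protocol set carries little formal weight. It is a sensitivity set, the 5% declaration sits in the primary endpoint analysis (SAP 11.1), and no success rule depends on it. The SAP defines the set and counts violators (10.1) but schedules no per-protocol analysis in 8.3, 11.1 or 11.2; the undertaking to repeat the analyses is the protocol's. The rejection rates above therefore measure how misleading the result could be. They are not the error rate of a trial decision. This stands, and it limits the severity.

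A reader might infer that the per-protocol result will certainly favour dornase alfa. The documents do not support that. Stopping is discretionary, some listed reasons need not track CRP, and the dexamethasone-order exclusion may pull the other way.

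A reader might also infer that leaving matched controls in place destroys the matching. SAP 6.2 is silent on what happens to them, and every propensity covariate (age, gender, BMI, baseline CRP, key comorbidity) is also in the outcome model. That adjustment softens the loss of matching, so the claim is too strong.

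The magnitudes rest on assumed stopping rates and CRP excesses in an unadjusted test, whereas the planned model is a repeated-measures one adjusted for baseline CRP.

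Finally, adherence criteria must fall on the arm that receives the drug. That is true, but stopping because of progression or toxicity is not non-compliance, and Protocol 8.8 itself lists the two separately. This last objection does not answer the point.

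**Conclusion.** The concern holds as an expected bias in a sensitivity analysis. The definition exposes the three groups unequally and, followed exactly, mixes treatment failure with non-adherence, so it cannot answer the question set in Protocol 11.3.4. The likely direction favours dornase alfa.

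The size cannot be derived from the documents. Under the stated assumptions it is about 3 to 17 mg/L, or 8% to 42% of the design difference, with rejection of about 6% to 19% when there is no drug effect. The adjusted model, replacement of withdrawals and the dexamethasone-order exclusion may all change these values.

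Nothing here shows the ITT-based primary conclusion to be wrong. The harm would come from treating a favourable per-protocol result as independent support for it. The change should be made but is not critical.

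**What to change.** Amend SAP 6.2. The change concerns the analysis set only and leaves the clinical stopping rules as they are.

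1. Limit the study-drug discontinuation and study-withdrawal exclusions to non-adherence unrelated to disease course.
2. Keep patients who stop for progression, toxicity, intercurrent illness or death.
3. When a dornase alfa patient is excluded, remove the two historical controls matched to that patient; 6.2 currently has no rule for this.
4. Tabulate per-protocol exclusions by reason and by group beside any per-protocol result. SAP 10.1 already plans counts of withdrawals, discontinuations and violations, so this extends an existing table.

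The cost is mainly wording. The set becomes a less pure on-treatment set and lies closer to ITT. The reason for stopping must also be available in the trial data. Protocol 8.8 requires reasons for clinical withdrawal to be recorded but names the CRF only for the decision, and participants who withdraw may withhold their reason. The SAP should say how an unknown reason is classified.
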